Patients with severe NBD impairment will be offered the adoption of TAI as a way to manage their own evacuation, replacing any other measure used until that moment (suppositoires, enemas) with the exception of the possible intake of macrogols and/or prebiotics and/or probiotics which instead can be continued. This treatment will be proposed to all patients with severe impairment of intestinal function.

The TAI training with Peristeen will be carried out at the surgical clinic of the Surgical Department of the Ferrara University Hospital, Italy, by the personnel involved in the study, usually in a single session, but more sessions may be necessary.

During the following 4 weeks, patients will continue to use the Peristeen at home according to the instructions provided by the training staff collecting a stool sample each week. During the last of the four weeks of TAI use patients will repeat the compilation of food diaries, evacuation diaries, the radiopaque markers Transit Time, and collection of the stool for microbiota analysis. The appointment for the radiography could coincide also in this case with the following visit (visit 3 or 4).

During the last visit the outcome of Transit Time X-ray will be discussed, completed diaries and stool samples will be collected, and PAC-QoL questionnaire will be submitted to patients who completed the study pathway.

Patients will be asked about overall satisfaction of TAI treatment with Peristeen by means of a numerical assessment from 0 to 10.

Finally, any comment will be noted as well any events that might be related to TAI irrigation with Peristeen will be recorded.

Patients will undergo a neurological examination 3 months after the start of treatment.

The whole duration of the study will be of 2 years.

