## **Intervention**

Patients with severe intestinal dysfunction impairment (PAC QoL score  $\geq 32$ ) will be offered the adoption of the TAI (Transanal Irrigation) with Peristeen Device as a way to manage their own evacuation, replacing any other measure used until that moment (suppositoires, enemas) with the exception of the possible intake of macrogols and/or prebiotics and/or probiotics which instead patients can continue. This treatment will be proposed to all patients with severe impairment of intestinal function.

The TAI training with Peristeen will be carried out at the surgical clinic of the Surgical Department of the Ferrara University Hospital, Italy, by the health personnel involved in the study, usually in a single session, but more sessions may be necessary, documented in CRF as VISIT 3, VISIT 3 bis and so on, until the end either with the continuation of the TAI independently for 4 weeks or with patient's exclusion from the study if the guarantees of appropriate use of the device will not be reached.

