## **Primary Outcome Measure:**

Outcome 1) Incidence and prevalence of intestinal dysfunction in Multiple sclerosis. Calculation of % of patients with a PACQoL score  $\geq 32$  for items B.1 to B.6 and/or a score  $\leq 11$  for item B.7 of the questionnaire.

Outcome 2) Characteristics of intestinal dysfunction in MS. Calculation of Agachan-Wexner scores, the Cleveland Clinic Index, the Altomare Questionnaire, and the NBD Score on the patient population that report a significant impact on their QoL of problems related to their bowel management and bowel disorders in general (Score  $\geq 32$  to PAC-QoL).

Outcome 3) Intestinal transit time in SM patients with intestinal dysfunction. Calculation of % of patients with a slowed Intestinal Transit Time ( $\geq 60$  hours for women and 55 hours for men)

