## **Statistical analysis**

Data will be expressed as median (interquartile range – IQR 25-75) and mean  $\pm$  standard deviation according to distribution assessed by Shapiro-Wilk test. Categorical data will be presented as numbers. Data will be analysed using Chi-square, t-student, and Mann-Whitney tests as appropriate. Cox regression analysis will be employed to assess independent predictors of improvement of intestinal dysfunction after Transanal Irrigation (TAI). Significance will be considered for values of  $p < 0.05$ . Statistical analysis will be performed with IBM SPSS Statistics for Windows, Version 24.0 (IBM Corp. Armonk, NY: IBM Corp.). The report will comply with the strengthening the reporting of cohort studies.

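### Cox regression is planned for predictors of improvement after TAI, but improvement is assessed only once, after a fixed 4-week period, so no time to improvement is observed

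*Combined protocol and SAP*

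**What the plan says.** The Statistical analysis section specifies: "Cox regression analysis will be employed to assess independent predictors of improvement of intestinal dysfunction after Transanal Irrigation (TAI". It names no event, time origin, censoring rule or method for ties. The other tests listed are chi-square, t and Mann-Whitney, so this is the only multivariable analysis in the plan.

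The schedule after TAI training is:

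- **Home period.** "During the following 4 weeks, patients will continue to use the Peristeen at home". The Intervention section gives the same fixed length: "until the end either with the continuation of the TAI independently for 4 weeks".
- **Diaries and transit time.** These are repeated once, in the last week: "four weeks of TAI use patients will repeat the compilation of food diaries, evacuation diaries, the radiopaque markers Transit Time".
- **PAC-QoL.** It is repeated once, at the last visit, in completers: "PAC-QoL questionnaire will be submitted to patients who completed the study pathway".
- **Date of the last visit.** It is not fixed to a day: "The appointment for the radiography could coincide also in this case with the following visit".
- **Training.** It is "usually in a single session, but more sessions may be necessary, documented in CRF as VISIT 3, VISIT 3 bis and so on".

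Secondary outcome 3 likewise describes TAI efficacy as a comparison of scores before and after the 4 weeks. The plan has dysfunction cut-offs: PAC-QoL of 32 or more, and, for "Calculation of % of patients with a slowed Intestinal Transit Time", 60 hours in women and 55 in men. Nowhere does it link them to improvement.

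**The concern.** A Cox model compares, at each event time, the patient who has the event with those still at risk. It therefore needs to know when each patient improved. Here the data can show only whether a patient had improved by about week 4. Any time entered in the model is either the same for everyone or an accident of scheduling.

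Two things are at stake. The result would be reported as a hazard ratio although no hazard was observed. And depending on the time and tie method chosen, the test can lose much of its power or, in one case, find an association that does not exist. With no event, origin or tie method fixed, these choices would be made after the data are seen, in a group drawn from at most 50 invited patients (Study population).

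**Working it through.** **1. Could anything in the schedule date an improvement?** The weekly item during TAI is a stool sample, not a bowel score. The evacuation diary during TAI covers only week 4, so it cannot date a change in weeks 1 to 3. Extra training sessions date training, not benefit. The 3-month contact is a neurological examination with no bowel scale named. So nothing does.

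**2. Inputs.** The documents give no improvement rate, number of TAI users, time origin or tie method, so there is no figure of the plan's own to reproduce. Everything below is assumed: a binary predictor split 50:50, N = 30 or 50, a two-sided 5% test and, for power, improvement rates of p − 0.2 and p + 0.2, where p is the overall proportion improved.

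**3. Case A: one common 4-week time.** There is a single risk set. With Breslow ties the coefficient is the log risk ratio, with model-based SE = √(1/e₁ + 1/e₀), where e is the number improved in a group of size n. The correct SE is √(1/e₁ − 1/n₁ + 1/e₀ − 1/n₀). With no effect, their ratio is about 1/√(1 − p).

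Example: 15/25 against 10/25 improved.

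- Cox, Breslow: ratio 0.60/0.40 = 1.50; SE = √(1/15 + 1/10) = 0.408; p = 0.32.
- Correct SE for the log risk ratio: √(1/15 − 1/25 + 1/10 − 1/25) = 0.294. The Cox SE is 0.408/0.294 = 1.39 times too large (approximation: 1/√0.5 = 1.41).
- Cox, Efron, same data: 1.74; p = 0.18.
- Logistic: odds ratio 2.25; SE = √(1/15 + 1/10 + 1/10 + 1/15) = 0.577; p = 0.16.

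So the reported hazard ratio is 1.50 or 1.74 according to a setting the plan does not state. By exact enumeration at N = 50, the true size of the nominal 5% Breslow test is 2.5%, 0.7% and 0.06% when 20%, 50% and 70% improve.

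**4. Case B: actual visit dates from the start of home use.** The last visit is taken as 0 to 6 days after day 28, with non-improvers censored at their visit (6,000 simulated trials). With no effect, false positives are 4.5–5.4% (Efron) and 2.6–4.1% (Breslow). But visit order is noise: it inflates the variance of the log risk ratio by about 1/(1 − p) near the null, and no tie method removes this.

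Power at N = 50, with the share of logistic power kept in brackets:

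| Improved overall | A, Breslow | A, Efron | B, Efron | Logistic (exact; simulated in B) |
|---|---|---|---|---|
| 30% | 0.818 (90%) | 0.911 (100%) | 0.811 (89%) | 0.911; 0.910 |
| 40% | 0.681 (79%) | 0.850 (98%) | 0.683 (78%) | 0.867; 0.874 |
| 50% | 0.556 (65%) | 0.798 (93%) | 0.592 (69%) | 0.859; 0.854 |
| 60% | 0.435 (50%) | 0.815 (94%) | 0.538 (62%) | 0.867; 0.866 |
| 70% | 0.314 (34%) | 0.883 (97%) | 0.495 (54%) | 0.911; 0.910 |

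At N = 30, Breslow in A keeps 73% down to 19% and Efron in B keeps 76% down to 43%. If visits spread over only 0 to 2 days, Efron in B keeps 93% down to 69% (N = 50) and 85% down to 55% (N = 30).

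**5. Case C: dates from the first training session.** As B, with 7 days added for an extra session and no true effect; 40% or 60% improved, N = 30 or 50, Efron ties.

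| Patients needing an extra session, by predictor group | False positives | Median hazard ratio |
|---|---|---|
| 10% and 10% | about 5% | – |
| 10% and 30% | 11–20% | 0.65–0.66 |
| 0% and 25% | 16–36% | 0.53–0.55 |

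The same data counted from the start of home use give 4.5–5.4%, and logistic regression gives 4.3–6.4%.

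**The case against.** The strongest reply is that the practical harm is small. The model can be run. With a common time and Efron ties little power is lost at a 40-point difference. In cases A and B the error costs power but does not raise false positives. Case C needs unequal training and 7-day gaps, which the documents do not give. No listed outcome depends on the model. All of this stands, and it limits the severity.

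The power figures can also be challenged:

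- **Effect size.** A 40-point difference is very large. For 20 points (N = 50, 50% improved, common time), power is 0.096 with Breslow, 0.258 with Efron and 0.336 with logistic. Efron then keeps 0.258/0.336 = 77%, so its small loss is not general. At N = 30 even logistic power is 0.183. Many missed predictors would therefore be due to sample size under any model.
- **Comparator.** The logistic score test has a true size of 6.5% at N = 50 and 50% improved, which flatters it. Against Firth logistic regression (power 0.811), Breslow in A keeps 0.556/0.811 = 69% and Efron in B keeps 0.592/0.811 = 73%.

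These points change the figures, not their direction.

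Two points affect the remedy. Outcome 1 adds an alternative criterion (11 or less on item B.7) to the PAC-QoL cut-off, so a definition of improvement must say whether it applies. And the Study Protocol section offers TAI for severe NBD impairment while the Intervention section uses PAC-QoL of 32 or more. Those passages must be reconciled, because they determine who is analysed.

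Finally, a smaller repair exists: keep a common time and use a robust variance. That is in effect robust Poisson regression for a risk ratio and is better named as such.

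**Conclusion.** The concern holds: the method does not fit the data the plan collects. This part rests on the documents alone and needs no simulation, because improvement is observed once, at about 4 weeks, and nothing supplies an event time.

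The size of the harm rests on assumed inputs. With a 40-point difference and N = 50, Cox keeps between 34% and 100% of logistic power, depending on the time entered, the tie method and the improvement rate. False positives rise only if time runs from the first training session and extra sessions are unequal between predictor groups. In A with Breslow ties and in B the estimate can be read as a risk ratio, exactly or nearly, but it would be mislabelled.

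This should be fixed before analysis. It does not affect the primary or secondary outcomes.

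**What to change.** Replace the Cox sentence with, for example:

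> *Predictors of the 4-week PAC-QoL score will be assessed, in patients who complete the 4-week TAI period, by linear regression on baseline PAC-QoL plus a few pre-named baseline predictors, giving adjusted mean differences with 95% confidence intervals.*

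If a yes/no improvement is kept:

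- **Definition.** Define it at 4 weeks by a named measure and threshold. Examples are the plan's PAC-QoL cut-off, or its transit-time cut-offs in patients who exceeded them before TAI.
- **Baseline.** Keep the baseline value as a covariate. Patients invited on PAC-QoL of 32 or more will in part fall below it by regression to the mean.
- **Model.** Use Firth logistic regression with profile-likelihood intervals (exact size 4.0–4.7% at N = 30–50 and 20–70% improved). Robust Poisson regression gives risk ratios but is conservative when improvement is rare: at 20% improved, size is 0.35% at N = 30 and 1.9% at N = 50.

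Either way, keep the predictors few and report how many TAI starters were not assessed at 4 weeks.

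**Cost.** For completers this is a change of wording and uses measurements already scheduled. The documents do not show whether the named software (SPSS 24.0) offers Firth regression, so this should be checked. The linear model changes the endpoint from improvement to a mean score; the yes/no option does not.

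Both options apply to completers only, as Cox would. Suppose 40% of starters improve in both predictor groups, and 30% against 10% of non-improvers drop out. Completers then show 0.4/(0.4 + 0.6 × 0.7) = 49% against 0.4/(0.4 + 0.6 × 0.9) = 43% improved, an odds ratio of 0.9/0.7 = 1.29 with no true difference. Including all starters would need further PAC-QoL collection or a stated missing-data method.
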